6.5. Week 52/Early Termination (ET)

If a subject discontinues the study, every attempt should be made to perform the required study-related ET and Post Treatment Week 4 visits and procedures.

Subject's Global Assessment, HAQ-DI and Pain Scale, FACIT- Fatigue, and SF-36 are recommended to be done before any other study procedures. Invasive study procedures such as blood draws should be done at the end of a study visit.

- Subject's global assessment
- HAQ-DI and Pain Scale
- FACIT-Fatigue and SF-36,
- WPAI-RA and EQ-5D, where available

- TSQM, when and where available
- Healthcare resource utilization questionnaire
- Complete physical examination
- Weight
- Vital signs
- SJC66/TJC68
- Physician's global assessment
- 12-Lead ECG
- Radiographs of hands, wrists, and feet

- Obtain blood samples for:
 - Hematology and Serum Chemistry
 - Lipid profile (fasting)
 - Serum CRP
 - Pregnancy test (serum required if subject is entering into LTE)
 - Blood sampling for PK
 - Biomarker blood samples
 - Quantitative Ig
 - vfpBMC and leukocyte subset samples (US and Canada only)
- Urinalysis (including pregnancy test if applicable)
- Urine stored for biomarker analysis
- Assessment of AE(s)/serious (S)AE(s) and concomitant medication
- Review Entry criteria for LTE (if applicable)

6.6. Post Treatment Week 4

The following procedures will be completed 4 weeks after the subject's last dose of study treatment. This visit is not applicable if the subject is continuing onto the LTE study.

- Symptom-driven physical examination
- Weight
- Vital signs
- Urinalysis (including pregnancy test if applicable)
- 12-lead ECG
- Obtain blood samples for:
 - Hematology and Serum Chemistry
- Urinalysis
- Assessment of AE(s)/SAE(s) and concomitant medication

6.7. Study Assessments

6.7.1. Efficacy

Efficacy assessments will be carried out at Day 1 and at Weeks 2, 4, 8, 12, 16, 20, 24, 30, 36, 44, and 52, or at ET (if applicable).

Assessments of RA will include the derived ACR (ACR20, 50, 70 as well as ACR-N and EULAR response criteria, DAS28 [CRP], CDAI, and SDAI as well as the individual components of the ACR response criteria [TJC68, SJC66], HAQ-DI, Physician's Global assessment, Subject's Global Assessment, Subject's Assessment of Arthritis Pain and CRP]) and radiographs of hands, wrists and feet (mTSS and mTSS components of erosion score and joint space narrowing).

Additionally, subjects will be asked to complete questionnaires, including the FACIT-Fatigue scale, SF-36, EQ-5D, TSQM, WPAI-RA at Day 1 and at Weeks 4, 12, 24, 36, and 52, or at ET (if applicable). Healthcare resource utilization will be assessed at the Day 1 and at Weeks 12, 24, 36 and 52, or at ET (if applicable).

6.7.1.1. Evaluation of Disease Activity: Tender and Swollen Joint Counts

Assessment of tender and swollen joints will take place at the time points indicated in the study procedures table ([Appendix 2](#)) and according to the assessments described in Section 6.4.

Each of 68 joints will be evaluated for tenderness and each of 66 joints will be evaluated for swelling (a list of joints to be evaluated is provided in [Appendix 7](#)).

An independent joint assessor with adequate training and experience in performing joint assessments will be designated at each study site to perform all joint assessments, and should be blinded to the other study assessments performed on that day. The joint assessor should preferably be a rheumatologist; however, if a rheumatologist is not available, it should be a health care worker with experience in performing joint assessments. The assessor should remain the same throughout the study per subject, as much as possible. It is required that the designated joint assessor identify an appropriate back up assessor to provide coverage if the designated joint assessor is absent.

6.7.1.2. Subject's Global Assessment of Disease Activity

The Subject's Global assessment of Disease Activity will be performed at the time points indicated in the study procedures table ([Appendix 2](#)). The Subject's Global assessment of Disease Activity should be completed before any other study procedures.

The Subject's Global Assessment of Disease Activity will be recorded on a 0-100 mm visual analog scale (VAS), with 0 indicating "no arthritis" and 100 indicating "severe arthritis".

6.7.1.3. Physician's Global Assessment of Disease Activity

The Physician's Global assessment of Disease Activity will be performed at the time points indicated in the study procedures table ([Appendix 2](#)).

The Physician's Global Assessment of Disease Activity will be recorded on a 0-100 mm VAS, with 0 indicating "no disease activity" and 100 indicating "maximum disease activity". The evaluating physician and the subject should complete the global assessments independently of each other.

6.7.1.4. Serum CRP

The subject's serum CRP will be measured at the time points indicated in the study procedures table ([Appendix 2](#)).

6.7.1.5. Health Assessment Questionnaire – Disability Index and Pain Scale

The functional status of the subject will be assessed using the HAQ-DI at the time points indicated in the study procedures table ([Appendix 2](#)) and should be completed before any other study procedures. The HAQ-DI is a 20-question instrument that assesses the degree of difficulty a person has in accomplishing tasks in 8 domains (dressing, arising, eating, walking, hygiene, reaching, gripping and errands/chores). Responses are scored on a 4-point Likert scale from 0, indicating no difficulty, to 3, indicating inability to perform a task in that area. The need for aids or help from another person will also be recorded. The HAQ-DI total score ranges from 0 to 3 with higher scores indicating greater dysfunction.

As part of the HAQ-DI, subjects will be asked to assess their average pain during the last week on a 0-100 mm VAS, with 0 indicating "no pain" and 100 indicating "severe pain". This assessment should be completed before the joint examination. This pain score will be used to drive the ACR20/50/70.

6.7.1.6. FACIT - Fatigue Scale

The FACIT-Fatigue scale (version 4) will be completed at the time points indicated in the study procedures table ([Appendix 2](#)) and should be completed before any other study procedures where local language questionnaires are available.

The FACIT-Fatigue scale measures an individual's level of fatigue during their usual daily activities over the past week. It consists of 13 questions with a 7-day recall period on a 5-point Likert scale, with 0 indicating "not at all" and 4 indicating "very much". The total score ranges from 0 to 52. Higher scores indicate a better the quality of life.

6.7.1.7. 36-Item Short-form Health Survey

The SF-36 (version 2) will be completed at the time points indicated in the study procedures table ([Appendix 2](#)) and should be done before any other study procedures.

The SF-36 is a health related quality of life instrument consisting of 36 questions belonging to 8 domains in 2 components and covers a 4-week recall period:

- physical well-being: 4 domains: physical functioning (10 items), role physical (4 items), bodily pain (2 items), and general health perceptions (5 items)
- mental well-being: 4 domains: vitality (4 items), social functioning (2 items), role emotional (3 items), and mental health (5 items).

The remaining item (health transition) is not part of the above domains but is kept separately. These scales will be rescaled from 0 to 100 (converting the lowest possible score to 0 and the highest possible score to 100), with higher scores indicating a better quality of life.

6.7.1.8. EuroQol 5 Dimensions

The EQ-5D questionnaire will be completed at the time points indicated in the study procedures table ([Appendix 2](#)) and should be completed before any other study procedures where local language questionnaires are available.

The EQ-5D is a standard measure of health status developed by the EuroQol Group to provide a simple, generic measure of health for clinical and economical appraisal {[The EuroQol Group 1990](#)}. The EQ-5D is not disease specific and has been validated in numerous health states.

The tool consists of the EQ-5D descriptive system and the EQ VAS. The descriptive part comprises 5 dimensions (mobility, self-care, usual activities, pain/discomfort, and anxiety/depression). Each of these 5 dimensions has 3 levels (no problem, some problems, and severe problems). Results for each of the 5 dimensions are combined into a 5-digit number to describe the subject's health state. The VAS records the subject's health on a 0-100 mm VAS scale, with 0 indicating "the worst health you can imagine" and 100 indicating "the best health you can imagine".

6.7.1.9. Work Productivity and Activity Impairment

The WPAI-RA is a questionnaire developed to measure impairments in work activities in subjects with RA {[Zhang et al 2010](#)} and will be completed at the time points indicated in the study procedures table ([Appendix 2](#)) and should be done before any other study procedures where local language questionnaires are available.

The questionnaire consists of 6 questions (currently employed, work time missed due to RA, Work time missed due to other reasons, hours actually worked, degree RA affected productivity while working [0-10 VAS; with 0 indicating no effect and 10 indicating RA completely prevented the subject from working], and degree RA affected productivity in regular unpaid activities [0-10 VAS; with 0 indicating no effect and 10 indicating RA completely prevented the subject's daily activities]). The recall period for questions 2 to 6 is 7 days.

Four main outcomes (expressed in percentages) can be obtained from the WPAI-RA: percentage of work time missed due to RA, percentage of impairment due to RA, percentage of overall work impairment due to RA, percentage of activity impairment due to RA. Note that for subjects who did not work during the 7 days covered by the WPAI-RA, the percent overall work impairment will be equal to the percent of work time missed due to RA.

6.7.1.10. Healthcare Resource Utilization

The Healthcare Resource Utilization Questionnaire is designed to assess healthcare usage during the previous three months across a number of direct medical cost domains.

This questionnaire should be completed by the patient prior to any procedures being performed at the visit, if possible where local language questionnaires are available.

6.7.1.11. Hands, Wrists, and Feet Radiographs

Hands, wrists, and feet radiographs will be taken at the time points indicated in the study procedures table ([Appendix 2](#)). Note that if a subject discontinues the study early and has had X-rays performed in the <12 weeks prior to discontinuation, these do not need to be repeated at ET. Radiographs performed after enrollment may be done +/-7 days of the scheduled visit.

All subjects who discontinue from investigational therapy but continue study visits and procedures, should continue to have radiographs performed as outlined in the study procedure table ([Appendix 2](#)).

The radiographs will be evaluated through central review by 2 independent blinded assessors using the mTSS.

6.7.1.12. Exploratory Patient Reported Outcomes

CCI
[Redacted text block]

6.7.1.13 Treatment Satisfaction Questionnaire for Medication (TSQM)

The TSQM will assess the overall level of satisfaction or dissatisfaction with medication subjects are taking. Subjects will be asked to rate their treatment satisfaction at the time points indicated in the study procedures table ([Appendix 2](#)). The TSQM will implemented when and where local language TSQM are available.

6.7.2. Safety and Tolerability

Adverse events, physical examinations, vital signs, ECG and laboratory assessments (standard hematology, serum/plasma chemistry, and urinalysis) will be collected.

6.7.3. Clinical Laboratory Evaluations

The hematology and serum chemistry laboratory analyses will be performed at a central laboratory. Reference ranges will be supplied by the central laboratory and will be used by the investigator to assess the laboratory data for clinical significance and pathological changes.

Blood samples will be collected by venipuncture **CCI** in the arm at the time points indicated in the study procedures table ([Appendix 2](#)). In addition, urine samples for the clinical laboratory assessments will be collected. Subjects only need to be fasted at days where lipid profiling is scheduled.

Please refer to [Appendix 6](#) for table of Clinical laboratory tests.

The laboratory values outside the normal range will be flagged and clinical relevance will be assessed by the investigator. More frequent sampling as well as additional tests may be performed as deemed necessary by the investigator as indicated.

Note that in the case where clinically significant laboratory test results are a potential reason for discontinuation from the study drug and withdrawal from the study, retesting of the affected parameter(s) should be prompt (within 3 to 7 days) after the investigator has consulted with the medical monitor. A decision regarding subject discontinuation should be made after the results from the retest are available (see [Section 3.5](#) for additional information).

The details of sample handling and shipment instructions will be provided in a separate laboratory manual.

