For a complete list of study inclusion and exclusion criteria, please refer to Sections 4.2 and 4.3.

Main Eligibility Criteria

- 1) Male or female subjects who are ≥18 years of age, on the day of signing informed consent
- 2) Have a diagnosis of RA (2010 ACR/ EULAR criteria), and are ACR functional class I-III
- 3) Have ≥6 swollen joints (from a SJC66) and ≥6 tender joints (from a TJC68) at Screening and Day 1

- 4) Must meet at least one of the following parameters at Screening:
 - positivity for either RF or anti-CCP Ab per central laboratory
 - OR
 - Serum CRP \geq 4 mg/L based on central laboratory value
 - OR
 - \geq 1 documented joint erosion on radiographs of the hands, wrists or feet by central reading
- 5) Limited or no prior treatment with MTX, ie, no more than 3 doses of MTX \leq 25 mg each in their lifetime for the treatment of RA, with last dose at least 28 days prior to Day 1, and are an appropriate candidate for MTX therapy, as per investigator judgment

Study Procedures/
Frequency:

The subjects will visit the clinical study center at Screening, Day 1, Weeks 2, 4, 8, 12, 16, 20, 24, 30, 36, 44, and 52 or ET.

For those subjects not entering the LTE, a follow-up visit will be planned 4 weeks after the last dose of study drug (Post Treatment Week 4). Consequently, subjects are planned to be in the study for approximately 60 weeks.

During the Screening period, the subject's radiographs (hands, wrists, and feet) will be sent for blinded central scoring. In addition, information on demographics, medical history/concomitant diseases, prior and current RA medications will be collected. A physical examination, a 12-lead electrocardiogram (ECG), and clinical laboratory assessments will be conducted to determine the subject's eligibility for study participation. The screening window may be extended to up to 42 days prior to the Day 1 visit for subjects who require repeat collection of radiographs only.

At Day 1, after the subject's eligibility for the study has been confirmed, the subject will be randomized to receive one of 4 dosing regimens: filgotinib 200 mg q.d. plus MTX up to 20 mg weekly, filgotinib 100 mg q.d. plus MTX up to 20 mg weekly, filgotinib monotherapy 200 mg q.d. or MTX monotherapy up to 20 mg weekly.

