6.2.2. Day 1 Assessments

At Day 1, after the subject's eligibility for the study has been confirmed, the subject will be randomized into the study to receive one of four study dosing regimens.

Subject's Global Assessment, HAQ-DI and Pain Scale, FACIT- Fatigue, and SF-36 are recommended to be done before any other study procedures. Invasive study procedures such as blood draws should be done at the end of a study visit. The following will be performed and documented at Day 1 prior to dosing:

- Subject's global assessment
- HAQ-DI and Pain Scale FACIT-Fatigue and SF-36
- WPAI-RA and EQ-5D, where available

- TSQM , when and where available
- Healthcare resource utilization questionnaire
- Symptom-driven physical examination
- Weight
- Vital signs
- SJC66/TJC68
- Physician's global assessment
- Obtain blood samples for:
 - Hematology and Serum Chemistry
 - Lipid profile (fasting)
 - Serum CRP

- Biomarker blood samples
- Pre-dose vfpBMC and leukocyte subsets samples (US and Canada only)

CCI [REDACTED]

- Urinalysis (including pregnancy test, if applicable)
- Urine stored for biomarker analysis
- Review of concomitant medications
- Record any serious adverse events and all adverse events related to protocol mandated procedures occurring after signing of the consent form

[REDACTED]

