6.4. Week 2 through Week 44 Assessments

The following assessments will be completed at each visit or as specified. All assessments are summarized in the Study Procedures Table ([Appendix 2](#)).

Subject's Global Assessment, HAQ-DI and Pain Scale, FACIT- Fatigue, and SF-36 are recommended to be done before any other study procedures. Invasive study procedures such as blood draws should be done at the end of a study visit.

- Subject's global assessment
- HAQ-DI and Pain Scale
- FACIT-Fatigue and SF-36 at Weeks 4, 12, and 24

- WPAI-RA and EQ-5D at Weeks 4, 12, and 24, where available
- [REDACTED]
- TSQM at Weeks 12, 24 and 36, when and where available
- Healthcare resource utilization questionnaire at Weeks 12, 24 and 36
- SJC66/TJC68
- Vital signs
- Weight
- Complete physical examination at Week 24 (symptom-driven PE conducted at all other visits)
- Physician's global assessment
- 12-lead ECG at Weeks 12, 24, and 36
- Assessment of serious AE(s), (S)AE(s) and concomitant medication
- Obtain blood samples for:
 - Hematology and Serum Chemistry
 - Serum CRP
 - Pre-dose vFPBMC and leukocyte subset samples at Weeks 4, 8, 12, 24, and 36 (US and Canada only)
 - Blood sampling for PK at Weeks 4, 12 and 24
 - Biomarker samples at Weeks 4, 8, 12, 24, and 36
 - Lipid profile (fasting) at Weeks 12 and 24
 - Quantitative Ig at Week 24
- Radiographs of hands, wrists, and feet at Week 24
- Urinalysis at Week 24
- Urine stored for biomarker analysis at Week 12 and Week 24

- Urine pregnancy test (for women of childbearing potential, as defined per protocol). During the periods where study visits are every 6-8 weeks, women should continue to have pregnancy tests every 4 weeks, using home pregnancy urine tests, that will be provided to them. The site will call the subject every 4 weeks to obtain results of these pregnancy tests and will record the information in the source documents and CRF.

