### **7.2.1. Summaries of Numeric Laboratory Results**

Descriptive statistics of Baseline values, values at each postbaseline visit and change from Baseline at each postbaseline visit will be provided by treatment group for the following laboratory tests:

- Hematology
  - Hematocrit
  - Hemoglobin
  - Platelet count
  - Red blood cell count

- Mean corpuscular volume
- White blood cell (WBC) count
- Lymphocytes
- Monocytes
- Neutrophils
- Eosinophils
- Basophils
- Chemistry
  - Alanine aminotransferase (ALT)
  - Aspartate aminotransferase (AST)
  - Alkaline phosphatase (ALP)
  - Total bilirubin
  - Serum creatinine
  - Creatinine clearance by Cockcroft-Gault formula
  - Creatinine phosphokinase (CPK)
  - Glucose
- Lipid
  - Triglycerides
  - Total cholesterol
  - HDL
  - LDL
  - LDL/HDL ratio

A baseline laboratory value will be defined as the last measurement obtained on or prior to the date/time of first dose of any study drug. Change from baseline to a postbaseline visit will be defined as the visit value minus the baseline value. The mean, median, Q1, Q3, minimum, and maximum values will be displayed to the reported number of digits; SD values will be displayed to the reported number of digits plus 1.

Median (Q1, Q3) of the observed values for the laboratory tests specified above will be plotted using a line plot by treatment group and visit.

In the case of multiple values in an analysis window, data will be selected for analysis as described in Section 3.8.3.

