### **7.2.2.1. Treatment-Emergent Laboratory Abnormalities**

Treatment-emergent laboratory abnormalities are defined as values that increase at least 1 toxicity grade from baseline at any postbaseline time point, up to and including the date of last dose of any study drug plus 30 days for subjects who permanently discontinued study drug, or the last available date in the database snapshot for subjects who were still on treatment at the time of an interim analysis.

If the relevant baseline laboratory value is missing, any abnormality of at least Grade 1 observed within the time frame specified above will be considered treatment emergent.

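### Glucose has a fasting baseline but no fasting requirement at 8 of 11 on-treatment visits, and the SAP has no rule to separate the two kinds of draw

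*Protocol*

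**What the plan says.** **When subjects fast.** Protocol 6.7.3 says "Subjects only need to be fasted at days where lipid profiling is scheduled". Section 6.2.2 lists "Lipid profile (fasting" among the Day 1 blood samples, section 6.4 gives "Lipid profile (fasting) at Weeks 12 and 24", and section 6.5 adds a fasting lipid profile at Week 52/ET.

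**When glucose is drawn.** Protocol Appendix 6 lists glucose under general chemistry. Only the lipid panel is marked as fasting. The synopsis schedules clinic visits at Screening, Day 1 and "Weeks 2, 4, 8, 12, 16, 20, 24, 30, 36, 44, and 52 or ET". Section 6.4 opens with "The following assessments will be completed at each visit or as specified", and hematology and chemistry are listed there without named weeks, so they apply at every visit. Section 6.6 adds chemistry at Post Treatment Week 4. Hemoglobin A1c is measured at Screening only.

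**What the SAP does with it.** SAP 7.2.1 names glucose among the tests for which "Descriptive statistics of Baseline values, values at each postbaseline visit and change from Baseline at each postbaseline visit will be provided by treatment group", with a by-visit line plot. SAP 7.2.2.1 defines treatment-emergent abnormalities as "values that increase at least 1 toxicity grade from baseline at any postbaseline time point", up to 30 days after the last dose. SAP 7.2.2.3 classifies each subject by the most severe post-baseline grade. None of these sections sets a fasting condition or calls for a fasting flag. SAP 7.2 plans no formal testing of laboratory data.

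**The concern.** A fed or part-fed glucose value set against a fasting baseline can show a rise that reflects a meal. In the by-visit summaries the mean change could move up and down with the fasting rule. In the treatment-emergent and worst-grade tables, one non-fasting draw is enough to set a subject's category for the whole study.

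At stake is how a descriptive safety table is read. Serum glucose is the only scheduled on-treatment blood measure of glycemia, so no other blood test in the schedule would clarify a blurred glucose table. The documents already recognize fasting state elsewhere: Protocol 7.5.3 cites a non-fasting triglyceride elevation as an example of a Grade 4 value that may not be clinically significant. No such allowance is made for glucose.

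**Working it through.** The documents state no figure on glucose or fasting, so there is none to reproduce. The visit count comes from the documents; everything after it rests on assumptions.

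**1. Visit count.**
- Scheduled on-treatment visits: Weeks 2, 4, 8, 12, 16, 20, 24, 30, 36, 44, 52 = 11.
- Fasting lipid visits among them: Weeks 12, 24, 52 = 3.
- No fasting requirement: Weeks 2, 4, 8, 16, 20, 30, 36, 44 = 8; 8/11 = 73%.
- Through Week 24: 5 of 7. Counting Post Treatment Week 4: 9 of 12.

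**2. Share of abnormal results due to non-fasting draws.** Let pf be the chance of an abnormal glucose at a fasting visit and r·pf the chance at a visit without the requirement. Expected abnormal results per subject are 3pf + 8r·pf, of which 8(r−1)pf is the excess. The share is 8(r−1)/(8r+3).
- r = 1: 0%; r = 1.5: 27%; r = 2: 42%; r = 3: 59%.
- A share of one half needs 8r − 8 = 4r + 1.5, so r = 2.375.

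**3. Subjects with any abnormality** (visits taken as independent): 1 − (1−pf)³(1−r·pf)⁸. At pf = 2%, all 11 visits give 19.9% (r = 1), 32.1% (r = 2) and 42.6% (r = 3). The three fasting visits alone give 5.9%. The step from 5.9% to 19.9% comes from having more visits; only the rise beyond 19.9% comes from non-fasting draws.

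**4. Effect on an arm difference.** Suppose a drug doubles pf from 2% to 4%. Fasting visits alone give 11.5% against 5.9%, a risk ratio of 1.96. Power is shown only as a yardstick (400 per arm, two-sided 0.05), since no test is planned; on fasting visits alone it is 0.81.

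| All 11 visits | r = 1 | r = 2 | r = 3 |
|---|---|---|---|
| Drug adds the same absolute risk at every visit: risk ratio (power) | 1.82 (1.00) | 1.44 (0.98) | 1.28 (0.92) |
| Drug effect appears only at fasting draws: risk ratio (power) | 1.24 (0.37) | 1.13 (0.23) | 1.08 (0.16) |

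In the first row the ratio shrinks but power stays above the fasting-only 0.81, because there are more visits. In the second row the effect is strongly diluted.

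**5. Simulation on the glucose scale.** Assumptions: fasting mean 91 mg/dL, between-subject SD 8, within-subject SD 6. The meal effect at the 8 visits has (mean, SD) of (5,10), (10,12), (15,15) or (25,20), truncated at 0. Treatment-emergent means baseline at or below the cutoff and any later value above it. There were 400,000 subjects per scenario.
- No drug effect: mean change from baseline at the 8 visits is +7 to +26 mg/dL.
- Cutoff 100, no drug effect: 19% on 3 fasting visits, 35% if all 11 were fasting, 70% to 82% as planned. The upper limit in this model is the share with baseline at or below 100, Φ((100−91)/√(8²+6²)) = Φ(0.9) = 82%.
- Cutoff 100, drug adds 5 mg/dL: the arm difference is 18 points on fasting draws and 7 falling to 0 points as planned.
- Cutoff 110, same drug effect: 9 points on fasting draws; as planned, 17 and 10 points for the two smaller meal effects, 4 and under 1 for the two larger.
- Cutoff 100, only half of the 8 draws fed: 60% to 80% with no drug effect; arm difference 11 falling to 1 points.

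Inflation appears at both cutoffs. Loss of the arm difference at 100 comes largely from rates approaching the 82% ceiling, and with the smaller meal effects it reverses at 110.

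**The case against.** The strongest case against is that this is tolerable noise in a descriptive table.
- The arms are randomized, double-blind and share one fasting rule, so meals cannot favor an arm. This stands.
- Change from baseline is reported visit by visit, so Weeks 12, 24 and 52 remain fasting-to-fasting comparisons. This stands for scheduled visits with a Day 1 baseline; if Day 1 is missing, the baseline may be a Screening draw with no fasting requirement.
- Not being required to fast does not mean having eaten. This stands, and the half-fed run shows how the size falls.
- Grades come from CTCAE 4.03, which the protocol links but does not reproduce, so the cutoffs, and any fasting condition attached to the grades, cannot be checked here. This stands, and the cutoffs above are assumptions.
- Grade 3 or higher and marked abnormalities are tabulated separately, and the simulation does not assess them. This also stands.

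A reader might infer that meals cause most glucose abnormalities. The documents do not support that: more than half of abnormal results requires r above 2.375, and no rates are given. A reader might also infer that the plan hides any real drug effect, but at a 110 mg/dL cutoff the planned analysis separates the arms as well as or better than fasting draws under the smaller meal effects.

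Finally, replacing the all-visit tables with fasting-only tables would remove 8 of 11 visits from the treatment-emergent count. That objection is decisive against replacement, but not against an added summary.

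**Conclusion.** The point holds as an interpretability gap. From the documents alone: the usual baseline is fasting, 8 of 11 on-treatment visits carry no fasting requirement, and the SAP compares or grades all draws without regard to fasting state. Apparent rises and low-grade treatment-emergent rates can therefore be inflated in every arm, and the size of an arm difference may be distorted.

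How far depends on values the documents do not give: the grade cutoffs, the size of the meal effect, the share of draws that are actually fed, and whether a drug effect shows at non-fasting draws. Directional bias between arms, a majority of abnormalities due to meals, and general masking of a drug effect are not established. This is a cheap improvement to a descriptive safety output and does not touch the efficacy conclusions.

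**What to change.** In SAP 7.2.1 and 7.2.2:
- Add a separate fasting-glucose summary giving change from baseline and treatment-emergent grades from the scheduled fasting draws: Day 1, Weeks 12 and 24, and Week 52/ET.
- Select these draws by scheduled visit. The study-day windows would not do it: Table 3-1 can place ET and unscheduled draws in other visits, and the Week 12 lipid window in Table 3-3 runs from Day 2 to Day 127.
- State how a subject whose baseline is a Screening draw is handled in this summary.
- Label glucose from the other visits as fasting not required in the by-visit table and plot.
- Keep the all-visit treatment-emergent, Grade 3 or higher and marked-abnormality tables and the listings, so that no safety signal is dropped.

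Sampling does not change. The cost is a short SAP addition and one extra set of tables, with fewer time points than the all-visit version.
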